## **5 JUSTIFICATION FOR THE DESIGN OF THE CLINICAL INVESTIGATION**

Although cardiac pacing is recommended in population investigated in this study, there is still a number of them who experience syncopal recurrences despite pacing. A better understanding of physiology of syncopal reflex and the effect of cardiac pacing is needed. To this purpose, an exploratory study design without additional follow-ups after HUTT executed as per standard clinical practice was chosen. There are no endpoints in this study due to its exploratory design without statistical hypotheses to be tested. The in- and exclusion criteria are defined in a way to select patients from the BIOSync study for whom the performance of dual-chamber pacing with CLS was already documented allowing to better correlate new insights from this study with the benefit of therapy. A rationale for the chosen sample size is given in section 12.5.

All devices are CE-certified and used according to their indication and user manual. Therefore, the use in human subjects is justified.

## 6 BENEFITS AND RISKS OF THE DEVICE, CLINICAL PROCEDURE, AND CLINICAL INVESTIGATION

### 6.1 Anticipated clinical benefits

Participating subjects will benefit from an accurate programming of cardiac pacing and CLS function, based on the detailed evaluation of pacing activation during the reflex induced by the HUTT. This may help further prevent syncopal relapses.

### 6.2 Anticipated adverse device effects

No additional risks related to the CLS function or the equipment used for HUTT are expected resulting from the participation in the study. Study patients have already received pacemaker therapy according to current guidelines. Anticipated Adverse Device Effects (ASADE) associated with pacemaker therapy are described in section 19.8.

Participating patients will undergo HUTT as per standard clinical practice. No serious adverse events related to the HUTT are expected in literature except for known adverse effects of nitroglycerine. These may include: dizziness, weakness, palpitations, vertigo, headaches, nausea, vomiting, diaphoresis, syncope, hypotension, pallor, flushing, exfoliative dermatitis, drug rash (5-7).

### 6.3 Risk associated with participation in the clinical investigation

The investigational procedures performed during routine patient follow-up do not involve additional risks for the enrolled subjects. Participating patients will undergo a HUTT examination at enrollment visit according to their normal follow-up schedule. HUTT is a safe procedure and often considered as part of normal clinical practice in the study population, even after pacemaker implant, to predict response to or adjust therapy. There have been reported neither deaths nor severe complications during the tests.

Unauthorized access to patient data or inadequate data protection (e.g. submission of non-pseudonymized data to the sponsor representatives) are possible risks associated with the participation. BIOTRONIK undertakes technical and organizational measures to protect patient's data and adheres to applicable European data protection laws.

### 6.4 Possible interactions with concomitant medical treatments

No interactions are expected with medical treatments.

### 6.5 Steps to control or migrate the risk

Careful selection of participants and accurate conduction of HUTT according to the procedures described in section 9 will allow to minimize potential risks. The following measures shall be taken during a HUTT:

- Adherence to relevant medical guidelines
- Use of nitroglycerine during active phase of the HUTT
- Resuscitation equipment available and trained personnel during test procedures

Study staff will be trained at study start (Initiation Visit) and periodically re-trained if necessary.

### 6.6 Rationale for benefit-risk ratio

As no additional risks are expected in association with study procedures, as described in sections 6.2 to 6.5, expected benefits reported in section 6.1 outweigh risks. In addition, the knowledge gained from the study will help improve diagnosis and treatment of patients with reflex syncope and asystolic HUTT response.

## **7 OBJECTIVES AND HYPOTHESES**

### **7.1 Purpose of the clinical investigation**

The purpose of this study is to add knowledge to better understand the hemodynamic mechanisms underlying recurrent syncopal events and optimal pacing programming.

### **7.2 Objectives (Endpoints)**

This study will provide standardized, complete and quality controlled data sets with parameters that describe hemodynamic changes and their timing with respect to CLS pacing activation during reflex syncope induced by HUTT.

### **7.3 Hypotheses**

Due to the exploratory design of the study there are no statistical hypotheses (null/alternative hypotheses) associated with study objectives.

### **7.4 Risks and anticipated adverse device effects**

There will be assessments of risks and anticipated adverse device effects throughout the clinical investigation as described in section 19.

Anticipated adverse device effects and risks associated with participation in the clinical investigation are described in subchapter 6.2 and 6.3.

## 8 DESIGN OF THE CLINICAL INVESTIGATION

### 8.1 General considerations

#### 8.1.1 Design type of clinical investigation

The study is designed as a prospective, non-randomized, multi-center, observational acute study without additional follow-ups after HUTT execution.

#### 8.1.2 Measures taken to minimize or avoid bias

Accurate patient selection as described in section 8.2 and precise conduction of HUTT according to the procedures described in section 9 will allow to minimize potential confounding factors.

#### 8.1.3 Data of interest

- a) Heart rate, blood pressure, stroke volume, and peripheral resistance will be collected at the following time-points during HUTT:
  - time of maximum spontaneous heart rate (end of phase 1/beginning phase 2 of the reflex);
  - time of pacing onset;
  - time of recovery of spontaneous rhythm after pacing (end of recovery period);
  - time of syncope (i.e. loss of consciousness) during HUTT (also assessed by video recording if available at investigational site)
  - time of tilt-down (supine patient position just after tilt-down)
- b) Above-mentioned times of interest (expressed in HH:MM:SS from the start of the HUTT)
- c) Duration of the recovery phase (interval from maximum pacing rate to basic rate or spontaneous rhythm expressed in MM:SS from the start of the HUTT)
- d) Slopes in heart rate (bpm per sec) and systolic blood pressure (mmHg per sec) during the recovery phase

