## 2 SYNOPSIS

Title	BIO Sync-HUTT
Patient population	The study will select patients with reflex syncope and positive cardioinhibitory response to Head-Up Tilt Test (HUTT) who had already participated in the BIOSync study.
Design	Prospective, non-randomized, multi-center, observational, acute study.
Investigational device(s)	The closed-loop stimulation (CLS) algorithm implemented in current dual-chamber pacemakers manufactured by BIOTRONIK.
Objectives	To provide standardized, complete and quality controlled data sets with parameters that describe hemodynamic changes and their timing with respect to CLS pacing activation during reflex syncope induced by HUTT.
Data of interest	
a) Heart rate, blood pressure, stroke volume, and peripheral resistance at the following time-points during HUTT:
 
 
• Time of maximum spontaneous heart rate (end of phase 1/beginning phase 2 of the reflex);
 
• Time of pacing onset;
 
• Time of recovery of spontaneous rhythm after pacing (end of recovery period);
 
• time of syncope (i.e. loss of consciousness) during HUTT (also assessed by video recording if available at investigational site);
 
• time of tilt-down (supine patient position just after tilt-down);
 
 
b) Above-mentioned times of interest expressed as intervals (MM:SS) from the start of the HUTT
 
c) Duration of the recovery phase (interval from maximum pacing rate to basic rate or spontaneous rhythm expressed in MM:SS from the start of the HUTT)
 
d) Slopes in heart rate (bpm per sec) and systolic blood pressure (mmHg per sec) during the recovery phase

Title	BIO Sync-HUTT
Inclusion criteria	
 
• Ability to understand the nature of the study.
 
• Willingness to provide written informed consent.
 
• Patients undergoing HUTT for monitoring of syncope, therapy adjustment, training or other medical reasons during ordinary follow-up, irrespective of study participation.
 
• Patients who participated in the BIOSync study*.
 
• Patients with a dual-chamber pacing system equipped with the CLS algorithm.
 
 
* If needed, inclusion of other patients who did not participate in the BIOSync study will be considered to complete study cohort, provided that they have already a CLS pacemaker system and fulfill the same inclusion/exclusion criteria of the BIOSync study.

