#### **Definitions.**

Phase 1 of reflex during HUTT is defined as the interval from the start of blood pressure decrease due to a reduced venous return (and consequent corrective heart rate increase) to the beginning of phase 2.

Phase 2 is characterized by decrease of heart rate due to the activation of vagal reflex. Phase 2 (HR drop) may be partially masked by pacing activation.

Recovery phase is defined as the interval from maximum pacing rate to basic rate or spontaneous rhythm, if pacing is not delivered.

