10.2 HUTT

Data file: Identifier patient_ display_id_full	Notes	Variable name	Variable label	Variable level	Nominal values
hutt	Case listing	CVMHRITM	Time of maximum spontaneous heart rate (end of phase 1/beginning phase 2 of the reflex)	Scale	n.a.
	descriptive	QSHUPMPC	Did the pacemaker pace during HUTT?	nominal	o Yes o No
	Case listing	PRPCSTTM	Time of pacing onset/maximum pacing rate	scale	n.a.
	Case listing	PRHRPCTM	Time of recovery of basic pacing rate or spontaneous rhythm after pacing (end of recovery period)	Scale	n.a.
	Case listing	PRHRHRTM	Time of recovery of starting spontaneous heart rate	Scale	n.a.

		(for QSHUPMPC = No)			
descriptive	QSHUSNC	Did syncope (i.e. loss of consciousness) occur during HUTT?	Nominal	n.a.	
Case listing	QSSNCTM	Time of syncope	Scale	n.a.	
Case listing	QSTDTM	Time of tilt-down (supine patient position just after tilt-down)	scale	n.a.	
descriptive	QSHRHRDU	Duration of the recovery phase (interval from maximum pacing rate to basic rate or spontaneous rhythm from the start of the HUTT) [sec]	Scale	n.a.	
descriptive	CVHRHUST	HR at HUTT start [bpm] (upright patient position just after tilt)	Scale	n.a.	
descriptive	CVMHRT	HR at time of maximum spontaneous heart rate (end of phase 1/beginning phase 2 of the reflex) [bpm]	Scale	n.a.	
descriptive	CVHRPC	HR at time of pacing onset/maximum pacing rate [bpm]	Scale	n.a.	
descriptive	CVHRAPC	HR at time of recovery of basic pacing rate or spontaneous rhythm after pacing (end of recovery period) [bpm]	Scale	n.a.	
descriptive	CVHRAPCN	HR at time of recovery of basic pacing rate or spontaneous rhythm after pacing not applicable	nominal	o True o False	
descriptive	CVHRHU	HR at time of syncope during HUTT [bpm]	Scale	n.a.	
descriptive	CVHRAHU	HR at time of tilt-down	Scale	n.a.	
descriptive	CVSBPHST	Systolic BP at HUTT start [mmHg]	Scale	n.a.	
descriptive	CVDBPHST	Diastolic BP at HUTT start [mmHg]	Scale	n.a.	
descriptive	CVSBPMHR	Systolic BP at time of maximum spontaneous heart rate (end of phase 1/beginning phase 2 of the reflex) [mmHg]	Scale	n.a.	
descriptive	CVDBPMHR	Diastolic BP at time of maximum spontaneous heart rate (end of phase 1/beginning phase 2 of the reflex) [mmHg]	Scale	n.a.	
descriptive	CVSBPPC	Systolic BP at time of pacing onset/maximum pacing rate [mmHg]	Scale	n.a.	
descriptive	CVDBPPC	Diastolic BP at time of pacing onset/maximum pacing rate [mmHg]	Scale	n.a.	

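### End of recovery is defined in two ways, the SAP pools paced and spontaneous endings without recording which occurred, and the recovery duration carries two time origins

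*Protocol*

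**What the plan says.** **Protocol**
- Synopsis, data of interest (a): heart rate, blood pressure, stroke volume and peripheral resistance are read at several time-points, one of them "Time of recovery of spontaneous rhythm after pacing (end of recovery period". Section 8.1.3(a) repeats this: "time of recovery of spontaneous rhythm after pacing (end of recovery period".
- Section 8.1.3(c): the duration of recovery is the "interval from maximum pacing rate to basic rate or spontaneous rhythm expressed in MM:SS from the start of the HUTT". Item (d) asks for slopes of heart rate and systolic pressure over the same phase.
- Definitions, following 8.1.3: "Recovery phase is defined as the interval from maximum pacing rate to basic rate or spontaneous rhythm, if pacing is not delivered".

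**SAP 10.2**
- The end time, PRHRPCTM, is "Time of recovery of basic pacing rate or spontaneous rhythm after pacing (end of recovery period". The end values (CVHRAPC, CVSBPAPC, CVDBPAPC, CVSVAPC, CVTPRAPC) are tied to the same point.
- The duration, QSHRHRDU, is labelled "Duration of the recovery phase (interval from maximum pacing rate to basic rate or spontaneous rhythm from the start of the HUTT) [sec". It comes from the hutt data file and is not marked as derived.
- The start time, PRPCSTTM, is "Time of pacing onset/maximum pacing rate".
- The two slopes are derived variables with no formula, although SAP 2.4 requires construction instructions for derived variables.

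**The concern.** A patient paced at the basic rate meets the wider definition but not the one in item (a). The two definitions coincide when spontaneous rhythm returns first and separate when the basic rate is reached first.

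In a paced ending, the end heart rate is set by programming. In a spontaneous ending, it is the patient's own. The stated objective is to describe haemodynamics and their timing relative to CLS pacing, so the difference matters. A summary that pools the two cannot be read as either, and the reading requested in item (a) is missing for one group.

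The duration has a second problem. An interval between two events does not need the start of the test as its origin. That origin belongs to the time-points in item (b). A site that takes the label literally could enter elapsed test time.

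**Working it through.** The documents give no figure on this point, so there is nothing to reproduce. The check compares the texts and then adds arithmetic on stated assumptions.

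**1. The definitions side by side**

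| Place | End of recovery |
|---|---|
| Synopsis (a); protocol 8.1.3(a) | own rhythm returns after pacing |
| Protocol 8.1.3(c) | basic rate or own rhythm |
| Definitions | basic rate or own rhythm, with a final condition about pacing not being delivered |
| SAP 10.2, end time and all end values | basic paced rate or own rhythm |

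The final condition in the Definitions could be a rule: basic rate for paced patients, own rhythm for unpaced ones. That reading conflicts with item (a), which concerns own rhythm *after* pacing. It also leaves unpaced patients with an interval that starts at a pacing rate they never had.

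**2. What pooling does to the end heart rate**

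Inputs: basic rate 50 bpm (protocol Table 2). Assumed: spontaneous endings average 80 bpm, and a fraction f of patients ends at the basic rate. Pooled mean = 50f + 80(1 − f).
- f = 0: 80 bpm
- f = 0.25: 72.5 bpm
- f = 0.5: 65 bpm
- f = 0.75: 57.5 bpm
- f = 1: 50 bpm

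The documents do not give f.

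**3. What the choice of end does to the slope in one patient**

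Input: maximum CLS rate 120 bpm (Table 2). Assumed: the basic rate is reached at 60 s, and own rhythm at 70 bpm returns at 120 s.
- Wider definition throughout: (50 − 120)/60 = −1.17 bpm/s
- Item (a) throughout: (70 − 120)/120 = −0.42 bpm/s
- End rate from (a), duration from (c): (70 − 120)/60 = −0.83 bpm/s

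With 120 s and 240 s instead, the three values are −0.58, −0.21 and −0.42 bpm/s. The SAP itself does not combine (a) with (c). The third line shows what could follow if a site reads the end values by the protocol's item (a).

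**4. The duration label**

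Assumed: a 60 s recovery that starts 5 to 35 min into the test. Entered as an interval, it is 60 s. Entered as elapsed time, it is 5 × 60 + 60 = 360 s up to 35 × 60 + 60 = 2160 s.

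If 19 of 20 patients have 60 s and one is entered as 1500 s (a recovery ending at 25 min), the mean is (19 × 60 + 1500)/20 = 132 s. The median stays at 60 s, and the maximum of 1500 s would show in the table.

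**5. Can the duration be checked?**

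The natural check is PRHRPCTM minus PRPCSTTM. If a site enters pacing onset in PRPCSTTM, the result exceeds the true duration by the time from onset to maximum rate. The SAP records no separate time of maximum pacing rate, so this excess cannot be seen. CVHRPC, the natural starting heart rate for a slope, carries the same merged label.

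**6. Unpaced patients**

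QSHUPMPC flags pacing, and PRHRHRTM gives a recovery time when the answer is No. These patients have no maximum pacing rate, yet neither the duration nor the slopes are restricted to paced patients.

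**The case against.** Much can be said for the plan.

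- **The SAP is internally consistent.** It applies one combined end to the end time, the end values and the duration, in line with the Definitions. A reader might infer that the SAP takes end values under one definition and duration under another. It does not. The contradiction lies within the protocol, and between protocol item (a) and the SAP.
- **The closing event need not change the slope.** A reader might hold recovery at 60 s, move the end rate from 50 to 75 bpm, and compare −1.17 with (75 − 120)/60 = −0.75 bpm/s. That compares two different rates of fall. On a straight fall from 120 to 50 bpm in 60 s, 75 bpm is reached at 45 × 60/70 = 38.6 s, and (75 − 120)/38.6 is again −1.17. A difference needs a non-linear course or a later return of own rhythm, as in step 3.
- **The type of ending can be partly inferred.** An end heart rate near 50 suggests pacing, and continuous ECG traces are kept. This is indirect, since an intrinsic rate may lie close to 50, and the SAP does not plan it.
- **Non-applicable cases are partly covered.** CVHRAPCN marks an end heart rate as not applicable, and missing data are not replaced. Neither rule states what happens to duration or slopes.
- **A literal misreading of the duration would probably be caught.** The text says interval, the SAP unit is seconds, elapsed end time has its own field, times are listed by case, and data are queried and reviewed. The mislabelling is real, but widespread entry of elapsed time is not something the documents show.
- **The study is exploratory**, with no endpoints or hypotheses and at most 20 patients. This limits the consequence but does not remove the contradiction in the data the study exists to provide.

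**Conclusion.** The point stands as an inconsistency that should be corrected. Protocol item (a) and the synopsis ask for one event, while the rest of the protocol and the SAP accept either of two. Following the SAP leaves item (a) undelivered for patients who reach the basic rate first, and it pools their end values and slopes with spontaneous endings without a variable to separate them. The duration carries two incompatible origins, and its start cannot be verified.

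The size is unknown. It depends on how often recovery ends at the basic rate and on how sites complete the form, and the documents give neither. The figures in steps 2 to 4 are illustrations that use the 50 and 120 bpm of Table 2 with assumed times and intrinsic rates. It would go too far to call the recovery results uninterpretable. Blood pressure, stroke volume and resistance are measured rather than programmed, and the pacing response is itself under study.

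**What to change.** 1. Use one end-of-recovery definition in the synopsis, protocol 8.1.3, the Definitions and SAP 10.2.
2. Add a CRF field for how recovery ended (basic paced rate or spontaneous rhythm). Show end values and slopes by it, as a descriptive table or a case listing.
3. Where the basic rate comes first, also read the time and values at the return of spontaneous rhythm from the existing continuous recording, with an entry for not reached.
4. Remove the reference to the start of the test from the duration in protocol 8.1.3(c), the synopsis and QSHRHRDU.
5. Record the time and values at maximum pacing rate separately from those at pacing onset. Derive duration as end time minus time of maximum pacing rate.
6. State the slope formulas from the same two points: (end value − value at maximum pacing rate)/duration, for heart rate and systolic pressure.
7. Limit duration and slopes to QSHUPMPC = Yes, and list unpaced patients separately.

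Cost: a few CRF fields read from data already recorded, with no change to device settings or the test itself. Protocol section 14 treats changes to procedures or data analysis as substantial, so ethics approval is needed. Splitting at most 20 patients gives small cells, which is acceptable in a descriptive table and avoidable with a case listing.

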#### **Definitions.**

Phase 1 of reflex during HUTT is defined as the interval from the start of blood pressure decrease due to a reduced venous return (and consequent corrective heart rate increase) to the beginning of phase 2.

Phase 2 is characterized by decrease of heart rate due to the activation of vagal reflex. Phase 2 (HR drop) may be partially masked by pacing activation.

Recovery phase is defined as the interval from maximum pacing rate to basic rate or spontaneous rhythm, if pacing is not delivered.

#### **8.1.4 Methods**

##### **8.1.4.1 CRFs**

All parameters and measurements that are recorded within the registry are documented on the corresponding electronic case report forms (CRFs) listed below. The investigator is required to use an electronic signature to approve the content of the data reported in the CRFs.

Following CRFs are used:

- Enrollment/Baseline Form
- Device Interrogation Form
- HUTT Form
- Adverse Event/Device Deficiency Form
- Study Termination Form

The corresponding time schedule is described in Section 9.

##### **8.1.4.2 Source Data Sheets**

For HUTT data collection the following Source data sheets (SDS) are recommended to be used:

- HUTT examination (preparation phase) SDS
- HUTT examination (execution phase) SDS

##### **8.1.5 Equipment to be used for the assessment of variables**

Implanted device and related equipment are described in Section 4.

Patients will undergo HUTT exam as per clinical practice during ordinary follow-ups irrespective of study participation. This test will require the use of standard CE-marked equipment, such as tilt tables and tools to electronically record continuous data on HR, BP, SV, and TPR. Time of syncope may be assessed also by video-recording (if available at the investigational site).

##### **8.1.6 Replacement of patients**

A total of 20 subjects who had been already enrolled in the BIOSync study will be asked to participate in the present BIO|Sync-HUTT study. If less than 20 BIOSync patients will accept to participate for any reasons, participants may be replaced until fully analysable data set will be collected from 15 participants.

Replacements will consist of patients who already received a dual-chamber pacemaker with the CLS function who meet the same subset of inclusion/exclusion criteria of the BIOSync study (8).

##### **8.1.7 Investigation sites**

The study will be conducted in at least 2 investigational sites that already participated in the BIOSync trial.

### 8.1.8 Completion of the clinical investigation

The study will be completed when the last visit of the last subject will be available and documented in the CRFs (as defined in section 8.1.4.1).

## 8.2 Patients

The intended patient population consists of all patients with reflex syncope and positive cardioinhibitory response to HUTT who had already participated in the BIOSync study. As described in section 8.1.6 replacements are allowed, if needed.

